3.1. Primary analysis

The primary statistical analysis will be an unadjusted comparison of 24-wk change in ACT between treatment groups. A linear mixed effects model will be used to model the change in ACT over time. A saturated means model, including indicators for each time point, treatment and treatment by time interaction, will be specified and a random effect for individual will be used to account for the repeated measurements over time. The 24-week treatment by time interaction term represents the difference in change in ACT between the treatment groups, i.e. the primary outcome. If the data are non-normal, then transformations and non-parametric alternatives (e.g. Wilcoxon Rank-Sum test comparing the raw differences from baseline to 24-weeks between treatment groups) will be explored. If imbalances in influential baseline variables are present, then secondary analyses using appropriate stratification or adjustments will be done. Sensitivity analyses using alternate mean and covariance structures will also be performed. Analyses will be done based upon principles of intention to treat, i.e. all data from all randomized participants will be included in the analysis.

Secondary analyses will focus on the effects of additional covariates including age, gender, site, BMI >40, baseline ACT score, and adherence with treatment. These models will build on primary analysis described above. Potentials risk factors will be added as a main effect to reduce variability and interaction effect to identify potential subgroup effects. Analyses using adherence measures will be performed to explore dose-response relationships.

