3.3. Sample size

The sample size for this pilot is based on the confidence interval approach recommended by Cocks and Torgerson for pilot clinical trials.²⁹ For the definitive trial, the planned sample size is 190 (95 participants on active drug, 95 on placebo), to provide 90% power to detect a difference of 2.8 in the changes in ACT score from baseline to 24 weeks for the roflumilast versus placebo, with a type 1 error rate of 5%, and a standard deviation (SD) of 5. The SD is based on prior data from studies by our research network, and previous publications.^{30,31} A pilot study of 28 to 34 participants provides 90% one-sided confidence limit to exclude a clinical important effect in a definitive trial if we see no effect in the pilot study, and so could inform the decision as to whether to proceed to the full definitive trial. We will inflate this to 38 participants to allow for possible loss to follow up.

Table: Recommended pilot sample size for continuous outcome measures*

Standardized effect size for main trial	Pilot Sample size (90% level)	Upper 90% one-sided confidence limit
0.5	28	0.4844
0.45	34	0.4397
0.4	42	0.3955
0.35	54	0.3488
0.3	74	0.298

* Adapted from Cocks & Torgerson (2013)²⁹

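### Section 3.1 adjusts for baseline factors through main effects in a model of ACT level, which cannot adjust or sharpen the 24-week contrast, and it leaves the subgroup interaction undefined

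*Combined protocol and SAP*

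**What the plan says.** Section 3.1 (Primary analysis) sets the mean model: "A saturated means model, including indicators for each time point, treatment and treatment by time interaction, will be specified". For the covariance, "a random effect for individual will be used to account for the repeated measurements over time". The result is then defined: "The 24-week treatment by time interaction term represents the difference in change in ACT between the treatment groups". That definition is correct only if the response is the ACT score at each visit and baseline is one of the visits, so this is a model of ACT level.

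The secondary analyses concern "additional covariates including age, gender, site, BMI >40, baseline ACT score, and adherence with treatment". On how these enter, the section says "These models will build on primary analysis described above", followed by "Potentials risk factors will be added as a main effect to reduce variability and interaction effect to identify potential subgroup effects". It names no factor-by-visit or factor-by-treatment-by-visit term, and it does not say what the interaction is with. The same section allows stratified or adjusted analyses when important baseline variables are imbalanced, and sensitivity analyses with other mean and covariance structures, but specifies neither.

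The visit table in Section 2.9 schedules asthma control at all seven visits (weeks -1, 0, 2, 6, 12, 18 and 24), with pills first distributed at week 0. Section 3.2 analyses continuous secondary outcomes in the same manner, so the wording may carry over to them.

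**The concern.** The sentence gives each added term a purpose, and in this model neither purpose is secured.

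The main effect is meant to reduce variability. The reported effect, however, is a within-person contrast between week 24 and baseline, and the random effect already absorbs stable differences between people. A factor that is constant over visits has nothing left to explain in that contrast. If the arms differ by chance on such a factor, and the factor predicts change in ACT, adding it as a main effect returns the unadjusted answer. A reader shown both results side by side would probably take their agreement as evidence of robustness.

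The interaction is meant to find subgroup effects. If it is factor-by-treatment only, the fitted 24-week change effect is forced to be equal in the two subgroups, and the term describes something else: a subgroup difference averaged over all visits, pre-drug visits included.

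**Working it through.** **Inputs.** From the documents: 38 participants allocated 1:1, so 19 per arm; seven visits, two of them before drug; seven centers; SD 5 (Section 3.3: "with a type 1 error rate of 5%, and a standard deviation (SD) of 5"), taken here as the SD of 24-week change. Under a random intercept this gives a residual variance of 25/2 = 12.5. Assumed, because the documents do not give it: within-person correlation r of 0.3, 0.5 or 0.7.

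**Plan's own figures.** None is stated for the covariate or subgroup analyses. The pilot table in Section 3.3 reproduces as 1.2816 × √(4/N): 0.4844 for N = 28 and 0.4396 for N = 34 (printed 0.4397).

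**1. Main effect, complete data.** The contrast is (active mean at week 24 − active mean at baseline) − (the same for placebo). A main effect adds βX to every visit of a person. Its contribution is β(X̄_A − X̄_A) − β(X̄_P − X̄_P) = 0. The closed-form standard error is 5 × √(2/19) = 1.622 with or without the factor. In 300 simulated trials per scenario (REML fits, six visits from week 0 to week 24, one binary factor), the largest shift in any trial was 0.0000 and the average standard error was the same with and without the factor (for example 1.622 and 1.622 at r = 0.5).

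**2. Main effect, 20% dropout.** The mean absolute shift was 0.060, 0.039 and 0.025 points at r = 0.3, 0.5 and 0.7. The standard error went from 1.732 to 1.731 at r = 0.3 and stayed at 1.747 at r = 0.5 and 0.7.

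**3. A factor that truly predicts change by 4 points (r = 0.5, complete data).** Main effect: shift 0.00. Factor-by-visit terms: mean absolute shift 0.50, and the standard error falls from 1.66 to 1.64.

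**4. What a factor-by-treatment term estimates.** It compares person means over the seven visits. As a fraction of the week-24 subgroup difference:
- immediate effect: 5/7 = 71%
- effect linear in weeks: (2 + 6 + 12 + 18 + 24)/24/7 = 62/168 = 37%

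**5. Chance pre-drug differences.** With no true subgroup effect, the share of this term's sampling variance explained by the pre-drug contrast (mean of V1 and V2) is [r + (1 − r)/7] / [r + (1 − r)/2]:
- r = 0.3: 0.400/0.650 = 62%
- r = 0.5: 0.571/0.750 = 76%
- r = 0.7: 0.743/0.850 = 87%

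With a single baseline visit the denominator is 1, and the share runs from 40% to 74% (42% to 75% if only six visits are modelled).

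**6. Error rates.** Criterion |estimate/SE| > 2, six visits. With no subgroup effect, the factor-by-treatment term rejected in 5% to 7% of trials. With a true 5-point difference at week 24 and complete data:

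| Term | Effect | r = 0.3 | r = 0.5 | r = 0.7 |
|---|---|---|---|---|
| Factor × treatment | immediate | 63% | 38% | 17% |
| Factor × treatment | linear | 25% | 12% | 10% |
| Factor × treatment × week 24 | either | 31–33% | 31–33% | 27–31% |

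**7. Precision of the week-24 subgroup contrast.** Even split, four cells of 9.5: √(4 × 25/9.5) = 3.24 points. For site there are 7 × 2 × 7 = 98 cell means from 38 people, with 38/14 = 2.7 people per arm per site. A single site's treatment effect has standard error 5 × √(2/2.71) = 4.3 points.

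**The case against.** The strongest reply is that the text says only that an interaction will be added. Because these models extend one in which the treatment effect is itself a treatment-by-time term, a factor interacting with that effect is naturally three-way. This stands: the three-way reading is open, and the fault on the subgroup side is that the term is not defined. It does not help the main-effect half, where the form and the purpose are both stated.

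A reader might infer that a factor-by-treatment term would mostly report baseline chance and produce false subgroup findings. The documents do not support that. The term carries a diluted treatment signal and its false-positive rate stays near nominal. The share due to pre-drug chance depends on a within-person correlation the documents do not give and on whether one or two visits serve as baseline. When the effect is immediate and the correlation is 0.3 or 0.5, the term rejects more often than the three-way contrast.

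A reader might also infer that subgroup results would set eligibility for the definitive trial. No section says so: Section 3.3 ties the decision to proceed to the ACT effect, and Section 2.10 to feasibility outcomes.

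The imbalance and sensitivity clauses in Section 3.1 could accommodate covariate-by-visit terms, but they do not call for them. The one method the section does describe is the main effect. It is also true that the gain in precision from the right terms is small and that no subgroup analysis of 38 people will be very informative.

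**Conclusion.** The point holds for baseline factors that are constant over visits. Entered as main effects in the Section 3.1 model, age, gender, site and BMI above 40 leave the 24-week contrast exactly unchanged with complete data and almost unchanged with dropout (0.02 to 0.06 points on average, against a standard error of about 1.7). The stated aim of reducing variability is therefore not met, and agreement between adjusted and unadjusted results would carry no information.

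The subgroup term is undefined. If it is two-way, it captures about 71% (immediate) or 37% (linear) of the week-24 difference, and much of its sampling variance comes from chance pre-drug differences: 62% to 87% with a V1/V2 baseline and 40% to 75% with one baseline visit, for assumed correlations of 0.3 to 0.7.

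The primary analysis, which is unadjusted, is not affected. Adherence is measured after randomization and baseline ACT is itself one of the modelled outcomes; the conclusion does not extend to either. The figures rest on a random-intercept model, on SD 5 being the SD of change, and on the assumed correlations.

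**What to change.** In Section 3.1:

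- **Adjustment.** State that adjusted models include covariate-by-visit terms for age, gender and BMI above 40. Alternatively, use the 24-week change as the outcome with these covariates. Center, if adjusted for, should enter only in that change model, because a center main effect in the repeated-measures model has the same defect.
- **Subgroups.** Define the estimate as the factor-by-treatment-by-week-24 contrast, with the lower-order terms included. Report it with a confidence interval and label it exploratory, noting a standard error of about 3.2 points for an even split of 38.
- **Site.** Do not fit site-by-treatment-by-time interactions.

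The cost is a few sentences of plan text and a few lines of model code, with no change to data collection. Each single-term covariate takes six extra degrees of freedom for its visit terms in the seven-visit model. The change model uses only participants with a week-24 score, and center takes six degrees of freedom there.

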3.2. Secondary outcomes

Secondary outcomes include ASUI, mAQLQ, and GSRS scores, lung function, weight loss and adverse events. Continuous outcomes, scores and lung function, will be analyzed similarly to the primary outcome. Event outcomes will be analyzed in two ways: negative binomial regression to estimate rates and Kaplan-Meier curves and Cox proportional hazard models for time-to-first event.

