1.2. Primary objective

The primary objective of this proposal is to perform a pilot placebo controlled trial of roflumilast for the treatment of poorly controlled obese asthmatics in select centers of the American Lung Association-Airways Clinical Research Centers (ALA-ACRC) to determine the effectiveness and tolerability of our intervention in obese asthma.

[figure not shown]
The current proposal comprises a pilot randomized, placebo-controlled trial of roflumilast in obese patients with poorly controlled asthma in five centers of the American Lung Association-Airways Clinical Research Centers (ALA-ACRC).

The results of this trial will lay the groundwork for a definitive multicenter clinical trial of roflumilast for the treatment of poorly controlled asthma in obese patients. If ultimately successful roflumilast would represent a new treatment for obese patients with asthma, a patient population refractory to current therapies that represents the majority of poorly controlled asthmatics in the United States.

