2.3. Rationale for dose of active drug

We base the dose of active drug on the dose that is FDA approved for use in COPD in this country, and has also shown efficacy in the treatment of asthma⁸ and metabolic disorders:¹⁰ this will be 500 µg, once per day. For the first two weeks we will treat with 500 µg every other day to increase tolerability of the medication.

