2.9. Procedures

Sites conducting remote follow up visits must use a secure (password protected) zoom link or other secure online communication method. Participants who are followed up remotely, will complete some questionnaires over the phone and mail back the rest of the questionnaires to the site.

Outline of Study Visits							
Week	-1	0	2	6	12	18	24
Visit number	V1	V2	V3	V4	V5	V6	V7
Consent	•						
Baseline/interim history	•	•	•	•	•	•	•
Randomization		•					
Pill distribution†		•		•	•		
Pill distribution‡		•			•		
Review of paper/electronic diary cards		•	•	•	•	•	•
Pill Counts			•	•	•	•	•
Asthma Control	•	•	•	•	•	•	•
Anxiety/depression questionnaires	•	•	•	•	•	•	•
GSRS	•	•	•	•	•	•	•
QOL	•	•	•	•	•	•	•
Anthropometrics	•	•	•	•	•	•	•
Fasting Blood draw¥		•					•
Pregnancy test*	•	•	•	•	•	•	•
End of study questionnaire							•

† if dose frequency is every day since V3

‡ if dose frequency is every other day since V3

¥ conduct blood draw only if site permits it

*for women of child-bearing potential and participating in remote follow up participants will be mailed testing kit, and asked to send photo of result to coordinator

- Participants will be trained on how to perform peak expiratory flow at the study visit and sent home with asthma action plan.
- Asthma paper/electronic diary cards will be completed by participants throughout the study to record daily morning peak expiratory flow (PEF), daily asthma symptom scores, beta-agonist use, nocturnal asthma awakenings, and health care use.^{17,18} Diary data are used to identify episodes of poor asthma control and days with no asthma symptoms (asthma-free days).
- The Asthma Control Test (ACT) is a 4-week recall questionnaire that measures asthma control.¹⁹
- The Marks Asthma Quality of Life Questionnaire (Marks AQLQ) assesses asthma specific quality of life.²⁰
- The Asthma Symptom Utility Index (ASUI) is a 2-week utility-weighted asthma symptom questionnaire.²¹
- GI side effects will be assessed with the Gastrointestinal Symptom Rating Scale. This is a 15-item instrument with five subscales (reflux, diarrhea, constipation, abdominal pain and indigestion) that was originally developed to assess the symptoms associated with the most common GI disorders, and has previously been used to assess tolerability of medications. The five subscales of the questionnaire produce a mean score ranging from 1 (no discomfort) to 7 (very severe discomfort).²²

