2.10. Rationale for outcome measurements

Our outcome measures are all well validated clinical outcomes for use in studies of asthma, and validated questionnaires for assessing likely side effects. We are including a number of feasibility outcomes that will inform the decision to proceed with a definitive multi-center clinical trial: these include assessment of recruitment and retention, adherence and non-compliance (from pill counts, diary cards, missed visits) and side-effects (from GSRS, PHQ-9 and GAD-7). Participants with scores on the PHQ-9 or GAD-7 that reach the thresholds for exclusion outlined in the eligibility criteria will be discontinued from study drug, the site specific plan for caring for these participants will be instituted, and they will be followed for the rest of the study off of study drug.

Baseline medical and asthma control questionnaires will take 20-30 minutes to complete, will be completed at the Medical Office Building, in a private office. Questionnaires are in paper format, and will be completed by the participant.

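### The GSRS result named in section 3.2 is the week-24 contrast, which leaves out GI symptoms at weeks 2–18 and can understate on-drug GI intolerance

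*Combined protocol and SAP*

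**What the plan says.** Section 1.2 states that the pilot is "to determine the effectiveness and tolerability of our intervention in obese asthma". Section 2.9 assigns GI symptoms to one instrument: "GI side effects will be assessed with the Gastrointestinal Symptom Rating Scale". The visit table schedules it at all seven visits. Section 2.10 lists the GSRS among the side-effect measures that will inform the decision on a definitive trial.

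The analysis is set by cross-reference. Section 3.2 lists GSRS scores as a secondary outcome and says: "Continuous outcomes, scores and lung function, will be analyzed similarly to the primary outcome". In section 3.1 the mean structure is: "A saturated means model, including indicators for each time point, treatment and treatment by time interaction, will be specified". Its named result is: "The 24-week treatment by time interaction term represents the difference in change in ACT between the treatment groups, i.e. the primary outcome". All data from all randomized participants are used, with no restriction to time on drug.

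On stopping, section 2.10 says of participants who reach the PHQ-9 or GAD-7 thresholds that "they will be followed for the rest of the study off of study drug". For GI symptoms, sections 4.1.1 and 4.3 require only discussion with the study doctor and the PI. The footnotes to the visit table also provide for some participants to be on every-other-day dosing after V3.

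No worst-score, any-visit, averaged or on-treatment GSRS summary is named, and no endpoint of stopping drug because of side effects.

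**The concern.** For ACT, a week-24 contrast that includes people who have stopped drug is a reasonable target: it asks what assignment to the drug achieves. For GI tolerability the question is different: how much GI discomfort does the drug cause while people take it, including those who cannot continue? A week-24 score from someone who stopped at week 6 does not answer that. If symptoms settle off drug, stopping because of GI symptoms pulls the contrast toward zero.

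At stake is the reading of the pilot. GSRS results feed the decision on a 190-participant trial. A small week-24 difference could mean that the drug was well tolerated, or that the participants with symptoms had come off it or cut down. The named contrast cannot separate the two.

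**Working it through.** **1. The plan's own tolerability figures.** Section 4.1.1 gives excess rates per 100 patient-years in earlier asthma trials and converts them to 24 weeks.

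- Diarrhea: 21.0 × 24/52 = 9.69, stated as 9.7%.
- Nausea: 24.0 × 24/52 = 11.08, stated as 11.1%.

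Both reproduce. Among the 19 participants on roflumilast (section 4.1.1) they imply 19 × 0.097 = 1.8 excess diarrhea cases and 19 × 0.111 = 2.1 excess nausea cases. These are cases, not stops. The documents give no stopping rate and no GSRS mean, SD or expected effect.

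**2. What the week-24 term uses.** In a saturated model with a random intercept and complete data, the week-24 interaction equals the difference between arms in mean change from baseline to week 24. A simulated data set checked this (19 per arm, six active participants off drug from week 12): the fitted model and the raw difference in change both gave 0.8325. Scores at weeks 2, 6, 12 and 18 therefore do not move the estimate. If some week-24 scores are missing, earlier scores enter indirectly through the random intercept, but the quantity estimated is still the week-24 difference.

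**3. Dilution under an equal effect.** Assumptions, not in the documents: everyone on drug has the same GSRS rise D, and k of 19 active participants stop and are back at the placebo level by week 24.

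Week-24 contrast = D × (1 − k/19)

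| k | share of D kept | lost |
|---|---|---|
| 1 | 95% | 5% |
| 2 | 89% | 11% |
| 4 | 79% | 21% |
| 6 | 68% | 32% |

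**4. Dilution when the stoppers are the symptomatic ones.** Assume instead that only k participants react, each with a rise of 3 points, and that all of them stop and recover. The early contrast is 3k/19: 0.32, 0.63 and 0.95 for k = 2, 4 and 6. The week-24 contrast is 0 in each case.

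**5. What averaging over V3–V7 does.** Take symptoms present at weeks 2 and 6 and gone at weeks 12, 18 and 24, with equal weight on the five visits.

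- Equal effect: share kept = 1 − (3/5)(k/19). For k = 2 this is 94%, for k = 4 it is 87%, against 89% and 79% at week 24.
- Only stoppers symptomatic: average = (2/5)(3k/19). For k = 2 this is 0.13, for k = 4 it is 0.25, against 0 at week 24.

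The average is still diluted, so it needs the early contrasts and the worst score beside it. Week 2 is the end of the initial period in which section 2.3 has drug taken "every other day to increase tolerability of the medication", so week 6 is the first GSRS visit after the move to daily dosing set out there.

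**The case against.** The strongest reply is that the GSRS is not the plan's only view of tolerability. Adverse events are asked about at every visit and rated in severity (section 2.9). They are analyzed by rate and by time to first event (section 3.2), and stopping later cannot erase a first event. Adherence and non-compliance are feasibility outcomes (section 2.10), and pill counts should show that drug was not taken. The saturated model already estimates the earlier contrasts, and section 3.2 does not forbid reporting them.

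Much of this stands, and it rules out several stronger readings:

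- **That people who stop for side effects are counted as tolerating the drug.** The plan has no tolerated/not-tolerated classification. What is true is narrower: a recovered score at week 24 carries no trace of the earlier symptoms in that contrast.
- **That PHQ-9 and GAD-7 share the problem.** They are not in the section 3.2 list, and section 4.2.1 makes a score past the threshold, or a rise of 5 or more from Visit 2, an adverse event. Such reactions are counted whatever the later off-drug score.
- **That off-drug follow-up after GI stops is laid down.** It is explicit only for PHQ-9/GAD-7 stops. For GI stops it is inferred from the intention-to-treat sentence.
- **That the contrast must fall as intolerance worsens.** If symptoms worsen in those who stay on drug, it rises.

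What remains is that none of the other measures uses the graded scale. Adverse events come from open-ended questions. Pill counts do not say why drug was missed, and where only remote visits are permitted they are made when bottles come back at the end of the study. Earlier GSRS contrasts can be estimated, but none is named, so choosing one later would be post hoc.

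**Conclusion.** The point holds for the GSRS. Its named result is the week-24 contrast in all randomized participants. With complete data that contrast ignores symptoms at weeks 2–18, and it can understate on-drug GI intolerance if participants stop or reduce drug and recover.

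The size cannot be fixed from the documents. Two to four stoppers among 19 would cost about 11% to 21% of the contrast, given an equal on-drug effect and full recovery by week 24. The loss is larger if the stoppers are the symptomatic ones, and complete if nobody else has symptoms. If few stop, or symptoms persist off drug, it is small.

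This does not invalidate the pilot, because adverse events and adherence partly cover tolerability. It should still be corrected, because the data are already scheduled and a better-aimed result comes from the model already planned.

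**What to change.** In section 3.2, take the GSRS out of the general sentence on continuous outcomes and specify:

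1. **GSRS tolerability result:** the between-arm difference in change from baseline averaged over V3–V7, with equal weight per visit, from the saturated model already planned, overall and by subscale.
2. **Reported beside it:** the week-2 and week-6 treatment-by-time contrasts, and the between-arm difference in each participant's worst post-randomization GSRS score, with a stated rule for missed visits.
3. **Supportive:** the week-24 contrast.
4. **Stopping:** the number and proportion per arm who permanently stop study drug, with reasons where recorded.

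The cost is some wording and a little more analysis; no visit or procedure changes. There are two limits. The worst score tends to rise with the number of visits completed, so unequal completion between arms would distort it; hence the rule for missed visits. The documents do not say that reasons for stopping are recorded, so item 4 may have to be a count alone unless a form already captures them.

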1.3. Study design

A 24 week, randomized, double-masked, placebo controlled trial in 38 participants.

1 week baseline ← 24 week treatment →

V1	V2	V3	V4	V5	V6	V7
wk-1	wk0	wk2	wk6	wk12	wk18	wk24

2. Methods

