2.6. Randomization and drug distribution

Participants will be randomly assigned with an equal allocation to receive either active treatment or matching placebo for 6 months. The treatment assignment will be double-masked, neither the participant nor the clinical center investigators will be informed of the treatment group. Randomization will be accomplished with an auditable, documented generation scheme that produces a reproducible order of assignment, this schema will be generated by the DCC. Randomization will be stratified by center and age and each clinical center randomization schedule will be based on randomly permuted blocks of varying size to ensure appropriate balance between the treatment groups within a center.

Drug bottles will be shipped to the centers from Temple University. These bottles will be identified by a number to maintain masking of the study site. Upon randomization, the site will be advised of the bottle number to issue a particular participant.

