4.1. Risks of Individual Procedures

4.1.1. Roflumilast

Roflumilast will be provided to 19 subjects for 24 weeks at the 7 centers. While roflumilast has been approved for use in patients with COPD, the label includes warnings about psychiatric events (including suicidality), weight loss, and drug interactions. The psychiatric adverse reactions included insomnia, anxiety and depression (rate of psychiatric adverse reactions was 2.6% higher in roflumilast group than placebo). Instances of suicidal ideation and behavior, including completed suicides, were observed in clinical trials and in the post-marketing surveillance of the drug, in individuals with and without any prior history of depression. Of note, the safety data for roflumilast were based on 4438 patients between the ages of 40-91 years, 73% of whom were male and 92.9% were Caucasian. Given these limitations (in comparison to the planned trial in patients with asthma), the safety risks are taken from a pooled analysis of asthma patients receiving the 500 mcg dose of roflumilast to be used in the current trial (n=1567; Chervinsky, P et al Pulmonary Pharmacology and Therapeutics 2015 (35):S28-34). (This asthma population was 42.2% male, 80.2% white, and had a mean BMI of 27.47 as well as including 96.7 % of subjects between the ages of 12-65 years. Treatment duration varied between 4-24 weeks.) In these studies of patients with asthma, the risks that occurred with more than 5 events per 100 patient years follow up in excess of the control group included:

Excess incidence rate of adverse events for roflumilast compared to placebo by System Organ Class (SOC)*:

- Gastrointestinal disorders (61.7 cases per 100 patient years)
 - Diarrhea (21.0 cases per 100 patient years)
 - Nausea (24.0 cases per 100 patient years)
- Psychiatric disorders (7.1 cases per 100 patient years)
 - Insomnia (6.0 cases per 100 patient year)
- Nervous system disorders (33.7 cases per 100 patient years)
 - Headache (20.8 cases per 100 patient year)
 - Dizziness (6.2 cases per 100 patient years)
- Musculoskeletal and connective tissue (19.8 cases per 100 patient years)
- Infections and infestations (19.2 cases per 100 patient years)

*Includes SOCs and the associated preferred terms for events with an excess of >5.0 cases per 100 patient years for the difference between roflumilast and placebo where 95% confidence interval does not include 0.

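### Section 3.2 gives adverse events only negative binomial and Cox models, with no level of analysis and no sparse-data fallback, so comparisons of individual terms and psychiatric events may have no finite ratio

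*Combined protocol and SAP*

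**What the plan says.** Section 3.2 of the combined protocol and SAP reads: "Secondary outcomes include ASUI, mAQLQ, and GSRS scores, lung function, weight loss and adverse events". Adverse events are the only event outcome in that list. Scores and other continuous measures follow the primary mixed model: "Continuous outcomes, scores and lung function, will be analyzed similarly to the primary outcome". Event outcomes are to be analyzed by "negative binomial regression to estimate rates and Kaplan-Meier curves and Cox proportional hazard models for time-to-first event". The section does not state the level at which adverse events enter these models. It also does not say what happens when an arm has few events or none. Section 3.1, by contrast, does name alternatives for the ACT analysis if the data are non-normal.

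The scale of the trial is given elsewhere. Section 1.3: "A 24 week, randomized, double-masked, placebo controlled trial in 38 participants". Section 2.6: "Participants will be randomly assigned with an equal allocation". Section 4.1.1: "Roflumilast will be provided to 19 subjects for 24 weeks at the 7 centers". The same section lists excess event rates over placebo from pooled asthma studies, for example "Psychiatric disorders (7.1 cases per 100 patient years", and converts five of them into anticipated excess percentages of patients over 24 weeks. It gives no placebo rates.

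**The concern.** Negative binomial and Cox models estimate log ratios and rely on large-sample standard errors. If one arm has no events, the log ratio has no finite estimate and the Wald interval is meaningless. If both arms have none, the ratio is undefined. With 19 participants per arm followed for under half a year, this can readily happen for a single adverse event term.

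Tolerability is part of the primary objective (section 1.2), and section 2.10 says side effects will inform the decision on a definitive trial. Section 4.1.1 states the expected harm as an excess percentage of patients. Section 3.2 plans no between-arm difference with an interval on that scale, so the pilot result for a term could not be set directly against the forecast.

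**Working it through.** **Inputs.** 38 participants at 1:1 give 19 per arm (sections 1.3, 2.6 and 4.1.1). Follow-up is 24 weeks. Excess rates per 100 patient-years (section 4.1.1) are diarrhea 21.0, nausea 24.0, headache 20.8, insomnia 6.0, dizziness 6.2, the psychiatric class 7.1 and the gastrointestinal (GI) class 61.7. Placebo rates are my assumption: 5, 10, 20 and 40 per 100 patient-years.

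**The plan's own figures.** Excess rate × 24/52 gives diarrhea 9.69, nausea 11.08, insomnia 2.77, headache 9.60 and dizziness 2.86. These round to the stated 9.7%, 11.1%, 2.8%, 9.6% and 2.9%, so all five reproduce.

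**Exposure.** 19 × 24/52 = 8.77 person-years per arm, at most. Section 3.3 states: "A pilot study of 28 to 34 participants provides 90% one-sided confidence limit". That range is 14 to 17 per arm, or 6.46 to 7.85 person-years.

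**Expected extra events on active drug**, rate/100 × 8.77: diarrhea 1.84, nausea 2.10, headache 1.82, insomnia 0.53, dizziness 0.54, psychiatric class 0.62, GI class 5.4. The five listed classes together have an excess of 141.5 per 100 patient-years, or 12.4 events.

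**Chance of an empty arm.** With Poisson counts, let b = exp(−placebo rate × 8.77) and a = exp(−(placebo rate + excess) × 8.77), rates per person-year. The chance that at least one arm is empty is a + b − ab. Example, diarrhea at a placebo rate of 10: b = exp(−0.877) = 0.416; a = exp(−0.31 × 8.77) = 0.066; result 0.416 + 0.066 − 0.027 = 0.455, or about 45%.

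| Assumed placebo rate | Diarrhea | Nausea | Headache | Insomnia | Dizziness | Psychiatric class | GI class | Expected number of the 5 terms with an empty arm |
|---|---|---|---|---|---|---|---|---|
| 5 | 68% | 67% | 68% | 78% | 78% | 77% | 65% | 3.6 |
| 10 | 45% | 45% | 46% | 56% | 56% | 55% | 42% | 2.5 |
| 20 | 20% | 19% | 20% | 26% | 26% | 25% | 17% | 1.1 |
| 40 | 3% | 3% | 3% | 5% | 5% | 5% | 3% | 0.2 |

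With 14 per arm the last column becomes 4.0, 3.1, 1.8 and 0.5. A whole class has a higher background rate than any one term in it, so the GI column should be read further down the table than the term columns. For GI, the active arm is empty with probability 0.4% even if the placebo rate is zero. The placebo arm is empty less than 10% of the time once its rate passes ln(10)/8.77 = 0.26 per person-year, about 26 per 100.

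**What an empty arm does to the planned models.** Fitting 0 versus 2 events gave a negative binomial log rate ratio of about 20 (standard error about 11,000) and a Cox log hazard ratio of about 30 (standard error about 2 million).

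**What stays finite.** The risk difference for 2/19 versus 0/19 is 10.5 points (Newcombe 95% CI −7.9 to 31.4). For 3/19 versus 0/19 it is 15.8 points (−3.9 to 37.6). An arm with no events in 8.77 person-years has an exact upper 95% limit of −ln(0.025)/8.77 = 3.69/8.77 = 0.42 per person-year, or 42 per 100.

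**The case against.** The strongest reply is that a reader might infer that tolerability as a whole goes unestimated, and the documents do not support that. GSRS is collected at every visit and, as a score, goes to the mixed model, so GI tolerability has a planned between-arm estimate. Section 2.10 also draws on PHQ-9, GAD-7, adherence and retention. Kaplan-Meier curves and arm-specific rates can be reported with an empty arm. They are absolute quantities, so it would also be too much to say that the absolute excess cannot be obtained. What is missing is a specified difference with an interval. This reply stands, and it confines the point to adverse event comparisons.

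Second, section 3.2 does not commit to one model per term. Pooled events would usually be estimable. In a simulation with dispersion 0.5 and the summed class excess, the negative binomial model converged in about 97% of trials at an assumed overall placebo rate of 50 per 100 patient-years, and in all of them at 100. For the GI class at 40 it converged in about 85%. This stands too, but the text leaves the choice open, and pooling would hide the individual and psychiatric risks that section 4.1.1 singles out.

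Third, a reader might infer that many event types will certainly have an empty arm. That depends on placebo rates the documents omit. It holds at about 10 per 100 patient-years or below and hardly at all at 40. Section 4.2.1 counts certain PHQ-9 and GAD-7 scores as adverse events, which could raise psychiatric counts in both arms.

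Fourth, poor convergence in simulation should not be read as showing that the ratio cannot be estimated. For diarrhea at a placebo rate of 20, both arms had events in 78% of simulated trials, but one package's negative binomial fit succeeded in only 37%. Most of the extra failures were dispersion reaching zero, where the model reduces to Poisson. Poisson with robust standard errors gave a finite ratio in every trial with events in both arms.

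**Conclusion.** The point holds for comparisons of individual adverse event terms and of psychiatric events. For these, the only between-arm methods named can fail to give a finite estimate, and neither the level of analysis nor a fallback is stated. The chance of this for a given named term runs from 67-78% at a placebo rate of 5 per 100 patient-years to 3-5% at 40. This range rests on assumed placebo rates, Poisson counts and full follow-up of 19 per arm. Loss to follow-up would raise it. The point does not extend to all tolerability information, nor to pooled or GI-class events unless background rates are low. It is an inexpensive change that should be made, not a flaw that undermines the trial.

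**What to change.** In section 3.2, state the level at which adverse events are analyzed. For each term and each system organ class, report by arm the number and percentage of participants with at least one event, and the risk difference with a Newcombe 95% CI. This matches the scale of the anticipated percentages in section 4.1.1. Add events per person-year by arm with exact Poisson limits. Keep the Kaplan-Meier curves as description. Limit negative binomial and Cox models to all adverse events combined, or to classes with events in both arms in sufficient number. The minimum should be set by the sponsor in advance, since the documents give no basis for a particular threshold.

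The cost is a few sentences and one standard table, with no extra data collection. The downside is that rare terms will have no model-based or covariate-adjusted ratio. The intervals will also be wide, as 3/19 versus 0/19 shows: they describe what a pilot of this size can and cannot exclude.
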